Pérez Rubio et al., 9 conducted a clinical trial in which BBR 500 mg V.O. every 8 h for 12 weeks in a population with metabolic syndrome, reported a significant decrease based on statistical tests in the values of TC (187.0 ± 33.3 vs 175.6 ± 27.0 mg / dL) and TG (215.9 ± 64.7 vs 131.1 ± 51.2 mg / dL), however, HDL-C and LDL-C did not change.

From the group of lipid-lowering drugs, bezafibrate has been a drug of choice for the treatment of hypertriglyceridemia and in combination with some other lipid-lowering drug for the treatment of mixed dyslipidemia.¹⁶

The safety and efficacy of bezafibrate make it a useful drug for the treatment of dyslipidemia, it is well tolerated and can be combined to achieve better control of mixed dyslipidemia. In turn, a meta-analysis of the use of bezafibrate in relation to the lipid profile, showed its effect in reducing the concentration of TC and TG and an increase in HDL-C levels, as well as a cardioprotective effect, which helped in reducing coronary heart disease by up to 28%.¹⁷

A clinical trial where bezafibrate was compared against placebo with a duration of 5 years in which 400 mg of bezafibrate were administered per day, showed a reduction in TG of up to 20.6 mg / dL without showing significant changes on TC, LDL-C, They also report an increase of up to 17 mg / dL of HDL-C.¹⁸

In the Mexican population, another clinical trial was carried out in patients with mixed dyslipidemia, to which bezafibrate was administered at a dose of 400 mg V.O. every 24 h for 12 weeks, it was reported that after treatment and when comparing with baseline values, TG were significantly reduced by 24.4% in the group that was administered bezafibrate (p <0.05), however, the rest of the lipid profile such as CT, HDL-C and LDL-C did not show a significant statistical

difference.¹⁶ This is the first study in which BBR was used in combination with bezafibrate as a therapeutic option for the treatment of mixed dyslipidemia.

HYPOTHESIS

The effect of the administration of the combination of BBR plus bezafibrate modifies the lipid profile in patients with mixed dyslipidemia.

OBJECTIVES

General

To assess the effect of the administration of the combination of BBR plus bezafibrate on the lipid profile in patients with mixed dyslipidemia.

Specific objectives

Determine the concentration of CT, TG, HDL-C, LDL-C, and VLDL-C before and after the intervention with BBR, bezafibrate and BBR plus bezafibrate.

Secondary objectives

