To determine the effect of the administration of BBR, bezafibrate and BBR plus bezafibrate on body weight, height, body mass index (BMI), waist circumference, blood pressure, fasting glucose, creatinine, uric acid.

Describe the tolerability of the administration of BBR, bezafibrate and BBR plus bezafibrate.

METHODOLOGY

To assess the effect of the administration of the combination of BBR plus bezafibrate on the lipid profile in patients with mixed dyslipidemia.

Specific objectives

Determine the concentration of CT, TG, HDL-C, LDL-C, and VLDL-C before and after the intervention with BBR, bezafibrate and BBR plus bezafibrate.

Study design

Single randomized, parallel group, double-blind clinical trial. Resident population of the Guadalajara Metropolitan Area between 30 and 60 years of age, of any sex, with a diagnosis of mixed dyslipidemia.

Study site

Institute of Experimental and Clinical Therapeutics (INTEC) located in the Department of Physiology, University Center for Health Sciences, University of Guadalajara.

The sample size was calculated according to the formula for clinical trials, 61 in which the following values were taken into account for its calculation: The Z_α corresponds to the value of statistical confidence, which was prefixed to a value of $Z_{1-\beta}$ of 95%, for a type I error of 5% expressed as a value of 0.05 with two tails. For this confidence, the value of Z was 1.96.

$Z_{1-\beta}$ that expresses the statistical power or power and was prefixed to the value of $Z-\beta$ of 80%, for a type II error of 20%, which is equivalent to a value of 0.20. For this statistical power and this type II error, the typified Z score was 0.842.

The expression δ refers to the standard deviation in the basal TG concentrations obtained from the BBR studies, which was 35 mg / dL.62 d is the expected TG difference of 44.2 mg / dl.36

The result was $n = 10$ for each intervention group, in order to ensure sufficient statistical power, the sample size was increased by 20% due to possible losses, giving $n = 12$ patients per group.

Inclusion criteria

The study population was selected based on the fulfillment of the following criteria:

Men and women, age completed: 30 to 60 years residents of the Guadalajara metropolitan area, ability to communicate and comply with the established requirements.

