Diagnosis of mixed dyslipidemia ($TG \geq 150 \text{ mg / dL}$ and $TC \geq 200 \text{ mg / dL}$), No drug treatment on lipid profile, signing of the consent letter under information.

People with suspected or confirmed pregnancy, lactating or puerperium, $TC \geq 400 \text{ mg / dL}$ were not included, $TG \geq 500 \text{ mg / dL}$, $BMI \geq 39.9 \text{ kg / m}^2$, DM2, Kidney and / or liver disease, Intolerance to bezafibrate or BBR, PAS / DBP $\geq 140 / 90 \text{ mmHg}$, consumption of drugs with known action on lipid profile, glucose metabolism, BP or body weight.

Elimination criteria. The withdrawal of informed consent, loss of follow-up, presence of a serious adverse event, adherence to treatment $<80\%$ were considered as a reason for exclusion, but not so in the final statistical analysis. Presence of any non-inclusion criteria during the intervention.

Variables

Independent variable

Pharmacological intervention:

Administration of 1500 mg of BBR homologated with 400 mg of placebo (calcined magnesia)

Administration of 400 mg of approved bezafibrate with 1500 mg of placebo (calcined magnesia)

Administration of 1500 mg of BBR with 400 mg of bezafibrate

Dependent variables

Primary: lipid profile (TC, TG, LDL-C, HDL-C, VDL)

Secondary: weight, height, BMI, WC, BP, glucose, creatinine and uric acid, as well as tolerability

Control variables

Diet: They were given general nutrition recommendations based on the provisions of the dietary and physical activity recommendations of the National Academy of Medicine of Mexico, as shown in ANNEX document.

Exercise: They were asked to continue with the daily physical activity they already did and not to increase it.

The patients who came voluntarily for clinical evaluation generally had some cardiovascular risk factor such as dyslipidemia, smoking, etc.

Groups, intervention allocation and blinding

Three groups were formed randomly which were integrated in the following way.

The first group of 12 patients with mixed dyslipidemia received O.V. one 500 mg BBR capsule and one 500 mg placebo capsule at breakfast, one 500 mg BBR capsule at lunch, and one BBR capsule and one 500 mg placebo capsule at night.

The second group of 12 patients with mixed dyslipidemia received one 200 mg bezafibrate capsule in the morning and one 500 mg placebo capsule, one 500 mg placebo capsule with food, and one 200 mg bezafibrate capsule and one of 500 mg placebo in the evening.

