Collection of blood samples for clinical chemistry analysis was performed by simple venipuncture in the anterior ulnar region at the height of the elbow crease, the procedure used to collect blood samples, as well as the volume of the It was established based on the activities required in each of the work visits. The total volume of blood required to collect during the entire field work was 10 ml per patient. The determinations of lipids, as well as glucose were carried out using colorimetric-enzymatic techniques as described below, as well as the expected intra- and inter-assay CVs based on the information provided by the

manufacturer (Biosystems) for each of the reagents and we use mg / dL as the unit of measure for all determinations.

TC: The serum concentrations of TC were determined by the method based on the use of three enzymes, TG: The concentrations of TG in blood were measured by a method based on the enzymatic hydrolysis of serum TG to glycerol and FFA by the action of LPL, HDL-C: Serum HDL-C concentrations were measured using a method based on a modification of the classical precipitation procedure using optimized amounts of polyvinyl sulfonic acid, LDL-C: The Fridewald formula $LDL-C = TC - (HDL-C + TG / 5)$ in mg / dL was used to calculate this value, VLDL: The $TG / 5$ ratio was used to calculate this value.

Glucose: it was determined using the glucose oxidase technique. The glucose in the sample is oxidized to glucuronic acid and hydrogen peroxide (H_2O_2) in the presence of glucose oxidase, CR: it was quantified by the Jaffé method, by means of which a reaction with picrate occurs in an alkaline medium, causing a complex colored, UA: It was measured by means of a technique that involves two reactions. All measurements were made automatically in the ERBA Mannheim XI 100 equipment, the reagents used were appropriate for each test and specific for each one.

STATISTIC ANALYSIS PLAN

The data obtained were expressed in measures of central tendency and dispersion for quantitative variables (mean and standard deviation) and for qualitative variables (frequencies and percentages). Statistical significance (p-value) was determined by:

When performing the normality test (Shapiro-Wilk) of the variables of the 3 groups, it was found that, among others, the TG did not present a normal distribution, therefore, for the interpretation of the results, non-parametric tests were used.

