Kruskal-Wallis test to identify differences between the three intervention groups in relation to the quantitative variables of the included participants.

Wilcoxon rank test to identify differences between the baseline and final evaluation of each intervention group in relation to the quantitative variables of the included participants.

Mann-Whitney U test to identify differences between two intervention groups in relation to the quantitative variables of the included participants.

X² test or Fisher's exact test to identify differences between two intervention groups in relation to the qualitative variables of the included participants.

The preset level to consider the probability obtained from any of the statistical methods used was $p \leq 0.05$.

All variables were analyzed with the SPSS v22 program for windows.

Recruitment

15 detection campaigns were carried out in different points of the metropolitan area of Guadalajara, in which 290 people were attended, who were asked if they suffered or were referred to suffer from any cardiovascular disease, dyslipidemia, diabetes, prediabetes, etc. They were determined if they had obesity by calculating the BMI and the WC was determined; A capillary glucose test was also taken, for which a One touch ultra-glucometer was used to discard, by way of scrutiny, any alteration related to glucose metabolism.

Of these patients, 60 reported having a dyslipidemia reference of their own or of a direct relative and were invited to the INTEC located at the University Center for Health Sciences of the University of Guadalajara to carry out a more complete scrutiny.

Scrutiny

Each patient was summoned to INTEC at 08:00 am with a 12-hour fast. The visit during the scrutiny period, like the rest of the scheduled visits, took place at INTEC from 8 a.m. During the first visit, a complete clinical record was integrated, for which a clinical interrogation and comprehensive physical examination were carried out, all the clinical characteristics required for the evaluation of the selection criteria for admission were corroborated. 5 ml of

venous blood were taken by venipuncture with an 18 Gy catheter in the brachial vein to determine the lipid profile (CT, TG, HDL-C) and glucose.

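### Five unranked primary lipids are each tested at p ≤ 0.05 with no deciding comparison, gate or familywise control, while the sample size rests on triglycerides alone

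*Combined protocol and SAP*

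**What the plan says.** - **Primary variables.** Variables (Dependent variables) lists "Primary: lipid profile (TC, TG, LDL-C, HDL-C, VDL") with no order or lead. VDL is evidently VLDL.
- **Hypothesis.** "The effect of the administration of the combination of BBR plus bezafibrate modifies the lipid profile in patients with mixed dyslipidemia". It names no lipid, comparator or direction.
- **Specific objective.** Lipid concentrations are to be determined "before and after the intervention with BBR, bezafibrate and BBR plus bezafibrate", that is, within each of the three arms.
- **Sample size (METHODOLOGY).** The error is set "for a type I error of 5% expressed as a value of 0.05 with two tails", with 80% power and a TG standard deviation of 35 mg/dL; "d is the expected TG difference of 44.2 mg / dl". The groups or time points that this difference separates are not named. The result is 10 per group, raised to 12 for losses.
- **Tests (STATISTIC ANALYSIS PLAN).** Kruskal-Wallis compares three groups and Mann-Whitney compares two. The third is "Wilcoxon rank test to identify differences between the baseline and final evaluation of each intervention group". One threshold covers all of them: "The preset level to consider the probability obtained from any of the statistical methods used was" p ≤ 0.05.
- **Derived lipids (Laboratory determinations).** "VLDL: The $TG / 5$ ratio was used to calculate this value". LDL-C is also calculated, from TC, HDL-C and TG.

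**The concern.** A 5% error was budgeted for a TG difference, but the plan then lets any of five primary lipids, in any listed test, reach significance at 5%. Nothing says which result decides the trial, or whether the combination must beat both single drugs or only one. Followed as written, the plan allows a chance difference from one single drug on one lipid to be reported as the combination modifying the lipid profile. A TG result would also appear a second time as VLDL.

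The within-arm tests add a separate problem. Every arm receives an active drug and nutrition advice, and no arm receives placebo alone. A significant before-and-after change in the combination arm therefore cannot show what the combination adds.

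**Working it through.** **1. Reproduce the sample size.** Inputs from METHODOLOGY: Z = 1.96 and 0.842, SD 35, difference 44.2.
- Two-group formula: 2 × (1.96 + 0.842)² × 35² / 44.2² = 2 × 7.851 × 1225 / 1953.64 = 9.85, so 10 per group, as stated.
- Paired or one-sample formula with the same SD: half of that, 4.92, so 5.

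The size therefore fits one two-sided, between-group TG test. This is inferred from the arithmetic. The document cites only a general formula for clinical trials.

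**2. Count the tests.** Per lipid: 1 Kruskal-Wallis + 3 Mann-Whitney + 3 Wilcoxon = 7. Five lipids give 5 × 7 = 35. Because VLDL is TG divided by a constant, its rank tests give the TG p-values again, apart from rounding ties. That leaves 4 × 7 = 28 distinct tests.

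**3. Error rate with no difference between arms.** The documents give no joint distribution for the lipids, so these inputs are assumptions:
- 12 per arm; TG lognormal, median 230, log-SD 0.3; TC 230 (SD 28); HDL-C 40 (SD 9); LDL-C = TC − HDL-C − TG/5.
- Three sets of correlations (TG–TC, TG–HDL-C, TC–HDL-C): (0.3, −0.4, 0.1), (0, 0, 0), (0.5, −0.6, 0).
- 20,000 simulated trials per set; exact Mann-Whitney (U ≤ 37, p = 0.0449); Kruskal-Wallis by chi-square.

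| Family tested at p ≤ 0.05 | Chance of at least one significant result |
|---|---|
| One named TG pair | about 4.5% |
| Any of the three TG pairs, no gate | about 11% |
| Combination vs either single drug, four lipids, no gate | 23–26% |
| The same, Kruskal-Wallis gating each lipid | 12–13% |
| All three pairs, four lipids, no gate | 31–34% |
| All three pairs, four lipids, Kruskal-Wallis gating each lipid | 14–16% |
| TG only, Kruskal-Wallis gate, any pair | 4.5–4.9% |

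The rates are two-sided. Counting only errors that favour the combination (lower TG, TC or LDL-C, or higher HDL-C), the third row becomes 12–14% and the fourth 6–7%. The within-arm Wilcoxon tests are in none of these figures.

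**4. The both-drugs rule.** Suppose one comparison is truly null and the other is always significant. This is the worst case for a rule that needs both. On TG alone the error is 4.3–4.6%, so no further adjustment is needed. Across the same three correlation sets, over any of four lipids it is 14–15% unadjusted, and 4.0–4.3% with Holm applied to the larger p-value of each lipid.

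**5. Power of the TG-led rule.** Protocol inputs, normal data, combination 44.2 below both single drugs, 40,000 trials. Kruskal-Wallis and both pairs significant: about 69% at 12 per arm and 57% at 10. Without the gate: about 70% and 57%, so the gate costs almost nothing. Holm over the four lipids, both pairs on TG: 46% and 33%.

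**The case against.** **TG is already the lead, because it sized the trial.** The sample-size paragraph is good support for choosing TG now. But the variables section makes all five lipids primary, and three ungated TG pairs alone give about 11%.

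**Kruskal-Wallis followed by pairwise tests is the natural reading.** It is plausible, and the plan does not exclude it. The plan does not state it either, so both readings are shown. A gate on each lipid still leaves 12–13% for the combination.

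**The highest figures overstate the problem.** This stands. A reader might infer that about one trial in three would yield a false primary success. The 31–34% includes BBR versus bezafibrate, which does not bear on a hypothesis about the combination. A reader might also treat the five lipids as independent, 1 − 0.95⁵ = 22.6%, and take that as the error rate. VLDL repeats TG and LDL-C is calculated, so that is not the trial's rate.

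**This is a first study of the combination, with a before-and-after objective.** An openly exploratory label would be legitimate, but the plan states a hypothesis and presets error and power. The within-arm tests answer the descriptive objective only.

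**The power figures are fragile.** This also stands. They assume normal data, although the plan reports that TG was not normal, and they use a baseline SD. With SD 51.2, the post-treatment value that BACKGROUND reports for a BBR trial in metabolic syndrome, power for both pairs is about 31% at 12 per arm and 23–24% at 10.

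**Conclusion.** The concern holds. The plan has no deciding lipid, comparison, gate or familywise control, and following its stated rule raises the chance of a false claim for the combination from about 4.5% to 23–26%, or to 12–13% under the gated reading. About half of the ungated errors would favour the combination. The exact rates depend on assumed distributions, but the inflation appears in every correlation set tried.

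Two further inferences are not supported. The first is that the TG test itself is mis-sized or inflated: 10 per group is reproduced, and one named TG pair keeps its error. The second is that endpoints were selected after seeing results. The plan does report a normality finding, but the blinding section says that the analyst did not know the treatments. The documents do not show when any ranking was chosen, because they contain none.

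**What to change.** 1. Base treatment claims on between-group tests, and say whether these use final values or changes from baseline, which the plan leaves open. Report the within-arm Wilcoxon tests as descriptive.
2. Report VLDL as TG/5 without a p-value.
3. Make TG the lead variable, because the trial was sized on it. Test Kruskal-Wallis first, then combination versus BBR and combination versus bezafibrate. Require both at p ≤ 0.05, in the favourable direction, to claim that the combination is better than each single drug.
4. Treat TC, LDL-C and HDL-C as secondary. If any confirmatory claim is made on them, test them after TG succeeds, with Holm adjustment.
5. Disclose that the sample-size paragraph is the only documented basis for TG as lead. Because the plan already reports data results, label the hierarchy post hoc unless a dated record shows that it preceded unblinding. Show Holm over the four lipids as a sensitivity analysis.

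**Cost.** Reanalysis of existing data and revised wording; no new data. Findings on the other lipids lose primary status. Power for both TG comparisons is about 69% at 12 per arm and 57% at 10, below the planned 80%, and 46% and 33% in the sensitivity analysis. These figures should be stated as illustrative.
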